#### **Confidentiality Statement**

Confidential

P1-CMS-01-US

Final 2.0 Amendment 1.0, 22-May-2017

Page 27 of 106

CSP

Related to PMI\_RD\_WKI\_000759

GGT	Gamma-glutamyl transferase
GOLD	Global Initiative for Chronic Obstructive Lung Disease
HIPAA	Health Insurance Portability and Accountability Act
HIV	Human immunodeficiency virus
ICF	Informed consent form
ICH	International Council for Harmonization
IRB	Institutional Review Board
IU	International units
LDH	Lactate dehydrogenase
LLOQ	Lower limit of quantification
MCH	Mean corpuscular hemoglobin
MCHC	Mean corpuscular hemoglobin concentration
MCV	Mean corpuscular volume
MDI	Metered dose inhaler
MedDRA	Medical dictionary for regulatory activities
NMC	Nasal mucociliary clearance
PMI	Philip Morris International
РР	Per protocol
ppm	Parts per million
PT	Preferred term
QC	Quality control
RBC	Red blood cell
RNA	Ribonucleic acid
RIN	RNA integrity Number
SAE	Serious adverse event
SAP	Statistical analysis plan
SD	Standard deviation
SOC	System organ class
SOP	Standard operating procedure

#### **Confidentiality Statement**

Confidential

P1-CMS-01-US

Final 2.0 Amendment 1.0, 22-May-2017

Page 28 of 106

Related to PMI\_RD\_WKI\_000759

SPT	Skin prick test
STT	Saccharin transit time
To	Time point of first product use during study day
TLC	Total lung capacity
UBC	United BioSource Corporation
WBC	White blood cell

# **Explanation of Terms**

The following special terms are used in this protocol:

- Cigarette The term 'cigarette' refers to commercially available cigarettes (manufactured) and excludes cigars, pipes, bidis, and other nicotine-containing products.
  End of study (EOS) The EOS for a study participant is defined as Discharge on Visit 3 plus the 1 day for the Safety Follow-up Period or the date of early termination of the study participant plus the 1 day for the Safety Follow-up Period. The EOS of the entire study is the end of the Safety Follow-up Period of the last study participant.
- Screening failure All screened study participants that are not enrolled because the fail to comply with inclusion/exclusion criteria are considered as screen failures.

# 1 ETHICS AND REGULATIONS

### 1.1 Institutional Review Board (IRB) Approval

Prior to the start of the study, the clinical study protocol, together with its associated documents (Informed Consent Form (ICF), subject information sheet, subject recruitment procedures (*e.g.*, advertisements), written information to be provided to the subjects, available safety information, the Principal Investigator's curriculum vitae (CV) and/or other evidence of qualifications and any other documents requested by the Institutional Review Board (IRB), will be submitted for review and approval to the relevant IRB. The IRB shall be appropriately constituted and perform its functions in accordance with the International Conference on Harmonization (ICH) Tripartite Guidance for Good Clinical Practices (GCPs) and local requirements, as applicable.

The written approval from the IRB will be filed in the Investigator Site File, and a copy will be filed in the study master file at the Sponsor or designated organization. The study must not start at a site before the Sponsor has obtained written confirmation of favorable opinion/approval from the concerned IRB.

Any substantial change or addition to this protocol will require a written protocol amendment that must be approved by the Sponsor and the Principal Investigator. All amendments will be submitted to the IRB, and substantial amendments will only be implemented after approval by the IRB. For modifications to the protocol which are administrative in nature, or do not affect subject risk, the IRB will be notified in writing by the Principal Investigator or designee with a copy provided to the Sponsor.

These requirements for approval should in no way prevent any action from being taken by the Principal Investigator or designee or by the Sponsor in order to eliminate immediate hazards to the subjects. If such a change to the protocol is felt to be necessary by the Principal Investigator or designee, and is implemented for safety reasons, the Sponsor and the IRB should be informed immediately.

The Principal Investigator is responsible for local reporting (*e.g.*, to the IRB) of SAEs that occur during the study, according to local regulations.

Relevant safety information will be submitted to the IRB during the course of the study in accordance with national regulations and requirements.

# **1.2** Ethical Conduct of the Study

The study will be performed in accordance with ethical principles that have their origin in the Declaration of Helsinki (World Medical Association, 2013) and is consistent with ICH/GCPs applicable regulatory principles.

The Principal Investigator or designee agrees to conduct the clinical study in compliance with the protocol agreed with the Sponsor and approved by the IRB. The Principal Investigator and the Sponsor must sign the protocol (and protocol amendments, if applicable) to confirm this agreement.

# **1.3** Subject Information and Consent

### **1.3.1** Informed Consent Form for Study Participation

Before or at Visit 1, the Principal Investigator or designee will ensure that each subject is given full and adequate oral and written information about the nature, purpose, possible risks and benefits of the study, and the Principal Investigator or the designee will answer all questions the subject might have to his full satisfaction. The subject will have sufficient time for consideration of his participation in the study and will be notified that he is free to discontinue his participation at any time.

### **Confidentiality Statement**

**Clinical Study Protocol** 

Confidential

P1-CMS-01-US

Final 2.0 Amendment 1.0, 22-May-2017

Page 32 of 106

Related to PMI\_RD\_WKI\_000759

Once the subject has received all the necessary information, and if he agrees to participate, this will be documented in the ICF which includes both the subject information sheet and informed consent by the date, and signature of both the subject and the person who conducted the Inform Consent discussion during Visit 1. No study-specific procedures will be performed before the ICF has been signed and date and time will be recorded.

The original and completed ICF(s) must be kept by the Principal Investigator and filed in the Investigator study file at the site or with the study participant's files and a copy must be given to the study participant. The study participant will be informed that if he discontinues from the study, the data collected until the point of discontinuation will be maintained as part of the study data and the samples collected prior to discotinuation will be analyzed, unless he refuses it.

The subject will be informed that any analysis of the data will be covered by data confidentiality.

### **1.3.2** Amendment to the Informed Consent Form

If a protocol amendment is required, an amendment may be required to the ICF. If revision of the ICF is necessary, the Principal Investigator or designee will, with the support of the Sponsor, ensure that the documents have been reviewed and approved by the IRB before study participants are required to re-sign and date the ICF.

### **1.4** Good Clinical Practice and Regulatory Requirements

The procedures set out in this clinical study protocol pertaining to the conduct, evaluation, and documentation of this study are designed to ensure that the Sponsor, its authorized representative, and Principal Investigator and designee abide by the principles of the ICH guidelines on GCPs. These guidelines apply specifically to pharmaceutical development, but nevertheless provide a robust and ethical framework for conducting clinical studies of tobacco products. The study will also be conducted in accordance with the general ethical principles outlined in the Declaration of Helsinki (World Medical Association, 2013).

### **Confidentiality Statement**

Data and information contained in this document are considered to constitute trade secrets and confidential commercial information, and the legal protections provided to such trade secrets and confidential information are hereby claimed under the provisions of applicable law. No part of this document may be publicly disclosed without the written consent of Philip Morris Products S.A.

Philip Morris Products SA	Clinical Study Protocol	Confidential
P1-CMS-01-US	Final 2.0 Amendment 1.0, 22-May-2017	Page 33 of 106

CSP

Related to PMI\_RD\_WKI\_000759

In addition, the Principal Investigator or designee will carry out the clinical study in accordance with applicable national and local laws of the pertinent regulatory authorities.

# **2** INTRODUCTION

### 2.1 Background

Tobacco smoke is a complex mixture of chemical compounds that are bound to aerosol particles or exist free in a gaseous state. It has been estimated that cigarette smoke has more than 6000 chemical compounds from various classes, the majority of which upon combustion can transform and have great potential for toxic, harmful, oxidizing, and carcinogenic effects (FDA, 2010, 2014). Cigarette smoke has been linked to increased risk of chronic pulmonary obstructive disease (COPD), cardiovascular disease, and cancer, which results in more than 480,000 deaths each year in the United States alone, and 1.2 million deaths annually worldwide (CDC, 2015; FDA, 2010). Despite widespread knowledge of the health risk associated with cigarette smoking, it is estimated that the prevalence of this habit is in excess of 1 billion people worldwide (CDC, 2015).

Gaseous and particulate constituents of cigarette smoke first interface with the immune system at the mucosal surfaces lining the oral cavity, sinuses, and the airways (FDA, 2010; Hecht, 2003). As the inhaled cigarette smoke moves deeper into the respiratory tract, more soluble gases are absorbed and particulates are deposited into the lower airways (Hecht, 2003). The carcinogens and toxins produced by cigarette smoke can provoke an array of biological and immunological responses in the respiratory tract. With sustained exposure, these inhaled constituents can lead to carcinogenesis induction, non-resolving inflammation yet suppressive effects on immune cells, mucociliary impairment, and innate and adaptive immune dysfunction (Jaspers, 2014; Lee, Taneja, & Vassallo, 2012).

There are a number of mechanisms involved in protecting the respiratory tract from harmful substances such as cigarette smoke. Beating, synchronized cilia function is the first line of innate host defense by propelling foreign inhaled substances, microbes, and/or mucus, out of the upper airways via nasal mucociliary clearance (NMC) (Fahy & Dickey, 2010; Shah, Ben-Shahar, Moninger, Kline, & Welsh, 2009). Several factors affect NMC including aging, temperature, mucus pH, drugs, smoking, body mass index (BMI), allergic rhinitis, and sinusitis

**Clinical Study Protocol** 

Confidential

P1-CMS-01-US

Final 2.0 Amendment 1.0, 22-May-2017

Page 35 of 106

Related to PMI RD WKI 000759

(Baby, Muthu, Johnson, & Kannan, 2014; Özler, Simsek, Akbay, & Akoğlu, 2014; Ramos et al., 2011, Paul 2016, Tamilselvan 2014, Balsamo 2010). A defect or impairment in ciliary motility, function, and consequently NMC, can cause increased airway inflammation, lung injury, bacterial colonization and eventually airway remodeling (Jain et al. 2012). Patients afflicted with diseases including cystic fibrosis (CF) and COPD have been shown to have impaired NMC function in their airway (Bhowmik, Chahal, Austin, & Chakravorty; Smaldone et al., 1993; Treacy, Tunney, Elborn, & Bradley, 2011). NMC measurement assesses the effectiveness of the interaction between cilia and mucus based on the measurement of (1) the transport of markers placed on the mucosa and (2) the total nasal clearance time of the deposited dose. There are a number of tracer molecules used to measure NMC time including saccharin, dye, and vegetable charcoal (Deborah & Prathibha, 2014). NMC strongly correlates with ciliary motility and function such that the greater the observed transit time, the further that ciliary motility and function is decreased (D. Passàli, Bellussi, & De Seta, 1984; D. Passàli & Bianchini, 1985; D. Passàli, Ferri, Becchini, Passàli, & Bellussi, 1999). Saccharin transit time (STT) is an inexpensive, non-invasive reproducible method that has been readily used to assess NMC (Stanley et al., 1984; Rutland & Cole, 1981). A positive correlation was observed between NMC, as determined by the STT test, and pulmonary clearance, measured by an inhaled radiolabelled aerosol (Loebinger, Bilton, & Wilson, 2009; Rutland & Cole, 1981).

Several authors have reported a decreased NMC in smokers versus non smokers and even passive smokers (Stanley et al., 1986, Habesoglu 2012, Utiyama et al., 2016). Moderate and heavy smokers show higher STT results than light smokers and non-smokers (Xavier et al., 2013). Decreased mucociliary function has been observed in people with moderate and heavy cigarette consumption (Proença et al., 2012). Smoking cessation appears to contribute favorably to mucociliary clearance (Ramos et al., 2011).

Proença et al. 2011 have studied the acute and short term effects of smoking on nasal mucociliary clearance in current smokers using the STT test immediately after smoking and 8 hours after the last cigarette. Smokers presented similar STT value immediately after smoking  $(11\pm6 \text{ min}; p=0.87)$  when compared to STT value in non-smokers' (10±4 min; mean±standard deviation), while the STT value in smokers 8 hours after smoking was significantly longer

**Clinical Study Protocol** 

Confidential

P1-CMS-01-US

Final 2.0 Amendment 1.0, 22-May-2017

Page 36 of 106

Related to PMI\_RD\_WKI\_000759

( $16\pm 6 \text{ min}$ ; p = 0.005 versus non-smokers' and p = 0.003 versus immediately after smoking), (Proença et al., 2011). The alterations of the STT value over time are not fully clear, as was demonstrated in the above study where no baseline measurement was reported. Therefore, based on this, the need for the present prefatory study and its proposed design is justified. In order to better understand the difference in STT over time between smokers and never smokers, a never smoker group is added to the study design.

Additionally, samples from nasal scrapings using two methods will be collected during the study from smokers and never smokers. These two methods will be used in this prefatory study to identify and standardize the optimal one which results in the highest quantity and quality of ribonucleic acid (RNA) for further transcriptomics analysis. The use of multi-omics have been used to elucidate mechanistic pathways which are impacted by cigarette smoking. The transcriptome of multiple tissues are known to be altered due to cigarette smoke exposure. Through targeted transcriptomic analysis from nasal sampling, increased expression and identification of antioxidant and xenobiotic genes as well as a wide spectrum of inflammation-related genes can be characterized. (Martin, Talikka, Hoeng, & Peitsch, 2015; Phillips et al., 2016; Titz et al., 2016).

## **2.2 Purpose of the Study**

This study intends to evaluate the NMC over the course of 12 hours following single use of cigarette in smokers, to compare NMC over the course of 12 hours in smokers following single use of cigarette relative to never smokers and to examine the relationship between plasma nicotine levels and STT value in smokers and never smokers.

Additionally it also intends to standardize a nasal scraping procedure using two methods with a histological assessment of nasal scraping and a RNA quality and quantity evaluation.

Safety will also be monitored during the study.

# 2.3 Anticipated Benefits and Risks

## 2.3.1 Anticipated Benefits

Subjects who participate in this study will benefit from a health check-ups, which may help to uncover undiagnosed medical conditions.

## 2.3.2 Anticipated Foreseeable Risks due to Study Procedures

The risk of procedures (*e.g.*, blood samples, nasal scrapes, spirometry) are deemed to be on par with procedures routinely performed during normal or extended health examinations by the study participant's health care professional. To monitor study participants for risks associated with study procedures after discharge, a follow-up period of 1 day is implemented.

## 2.3.3 Anticipated Foreseeable Risks due to Investigational Product

Not applicable.

# **3** STUDY OBJECTIVES

# **3.1 Primary Objectives and Endpoints**

The primary objectives of this study are:

1. To evaluate the NMC over the course of 12 hours following single use of cigarette in smokers.

• STT value as assessed by STT test at each time point.

2. To compare NMC over the course of 12 hours in smokers following single use of cigarette relative to never smokers.

• STT value as assessed by STT test at each time point.

3. To examine the relationship between plasma nicotine levels and STT value in smokers and never smokers.

• STT value as assed by the STT test and plasma nicotine levels at each time point.

# **3.2** Secondary Objectives and Endpoints

The secondary objectives of this study are:

- 1. To standardize nasal scraping procedure using two methods .
- Collection of nasal epithelium for further histology .
- Evaluation of RNA quality and quantity.

#### **Confidentiality Statement**

Data and information contained in this document are considered to constitute trade secrets and confidential commercial information, and the legal protections provided to such trade secrets and confidential information are hereby claimed under the provisions of applicable law. No part of this document may be publicly disclosed without the written consent of Philip Morris Products S.A.

Confidential

Page 39 of 106

Related to PMI\_RD\_WKI\_000759 CSP

- 2. To monitor the safety during the study.
- Vital signs.
- Adverse events (AE).
- Nasal and throat exam.
- Hematology, clinical chemistry and urine analysis.
- Brief physical examination.
- Concomitant medications.

# **4** INVESTIGATIONAL PLAN

# 4.1 Overall Study Design and Plan

This will be a single-center study in which 14 healthy adult male study participants, consisting of 7 cigarette smokers and 7 never smokers as a control group, will be enrolled. Study participants will not be replaced after being enrolled.

This study will have three visits on three separate days as described in Figure 1.

At Visit 1 (Screening Visit), study participants will undergo the procedures outlined in Appendix A to check eligibility criteria, including providing informed consent, undergoing a brief physical examination (including an examination of the head and neck, chest, heart (cardiovascular) and abdomen), nasal and throat exam, vital signs, skin prick test (SPT), spirometry testing, STT test, exhaled carbon monoxide (eCO) measurements, urine cotinine assessment, medical and smoking history and blood and urine collection for medical lab exams.

Following Visit 1, study participants who pass all of the inclusion criteria and do not present any of the exclusion criteria will be asked to return to the clinic for Visit 2.

During Visit 2, selected inclusion and exclusion criteria will be reassessed to ensure study participants are still eligible for enrollment (Appendix A). All study participants will have baseline assessments performed (Appendix A), including STT test.

Study participants will be confined in the clinic from the beginning of Visit 2 until discharge at Visit 3. During this confinement period study participants will abstain from drinking any alcohol and any drinks containing caffeine.

Water will be allowed *ad libitum* except during STT tests. Throughout the study, standardized meals and beverages will be served. Meals will be the same in content and quantity during each confinement period. No food or drinks will be allowed during STT tests.

No cigarettes are to be smoked from midnight ( $\pm 1$  hour) between Visit 2 and Visit 3 until 8 am on the day of Visit 3. On the day of Visit 3, at least 8 hours after last cigarette, cigarette smokers, who want to smoke, will have a cigarette at 8 am $\pm 30$  minutes and then have the STT

**Clinical Study Protocol** 

Confidential

P1-CMS-01-US

Final 2.0 Amendment 1.0, 22-May-2017

Page 41 of 106

Related to PMI\_RD\_WKI\_000759

test performed immediately after smoking (5-10 minutes post T0). T0 will be defined as the start of cigarette smoking for smokers (time point of first product use during study day). T0 should be the same for all smokers within an acceptable time window of 1 hour. Never smokers will also have the STT test performed in the morning at 8 am  $\pm$  30 minutes (designated T0 $\pm$  30 minutes). All study participants (smokers and never smokers) will then have the STT test performed until 4h30 min), 8h (may be performed until 8h30 min), and 12h (may be performed until 12h30 min) post T0, ensuring at least approximately 4 hours between the beginning of each STT test. The participant will be asked to confirm he can no longer feel the sweet taste. Study participants will drink a glass of water (approximately 240 mL) before STT tests are performed.

Samples for plasma nicotine assessment will be collected at approximately the same time points that STT test is performed at  $T_0$ , 4h (may be performed until 4h30 min), 8h (may be performed until 8h30 min), and 12h (may be performed until 12h30 min) post  $T_0$ .

Nasal scraping of the inferior turbinate of both nostrils will be performed on all 14 study participants at the end of Visit 3, after all other clinic assessments, except the brief physical examination which will be done after the nasal scraping:

- For 4 study participants, the nasal scraping (left nostril with method 1, right with method 2) will be performed and samples collected for subsequent histological assessment.
- For the 10 remaining study participants, 5 will undergo nasal scraping using method 1, and 5 using method 2. For all 10 study participants, cells from one nostril will be added into one buffer, cells from the other nostril into a second buffer. Samples will be collected for subsequent RNA quantity and quality analysis.

Full procedure is described in the "Method establishment to obtain human nasal epithelial sample using the Rhino-probe".

Upon conclusion of all clinic assessments, at the time of discharge on Visit 3, the Principal Investigator or designee will perform a brief physical examination on the study participant.

From the discharge on Visit 3, the study participant will enter a 1-day Safety Follow-Up Period during which spontaneously reported new AEs/serious AEs (SAEs) will be recorded, and the active follow-up of ongoing AEs/SAEs will be done by the site.

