**Clinical Study Protocol** 

Confidential

P1-CMS-01-US

Final 2.0 Amendment 1.0, 22-May-2017

Page 44 of 106

Related to PMI\_RD\_WKI\_000759

When compared to STT in non-smokers' ( $10\pm4$  min; mean $\pm$ standard deviation), smokers presented similar STT immediately after smoking ( $11\pm6$  min; p = 0.87) and slower STT 8 hours after smoking ( $16\pm6$  min; p = 0.005 versus non-smokers' and p = 0.003 versus immediately after smoking) (Proença et al., 2011). The alterations of the STT values over time is not fully clear as in the above study no baseline measurement has been reported and which establishes the need for the present prefatory study and justifies its proposed design. In order to better understand the difference in STT over time between smokers and never smokers, a never smoker group is added to the study design.

Additionally, samples from nasal scrapings using two methods will be collected during the study from smokers and never smokers. These two methods will be used in this prefatory study to identify and standardize the optimal one which results in the highest quantity and quality of ribonucleic acid (RNA) for further transcriptomics analysis. The use of multi-omics have been used to elucidate mechanistic pathways which are impacted by cigarette smoking. The transcriptome of multiple tissues are known to be altered due to cigarette smoke exposure. Through targeted transcriptomic analysis from nasal sampling, increased expression and identification of antioxidant and xenobiotic genes as well as a wide spectrum of inflammation-related genes can be characterized. (Martin, Talikka, Hoeng, & Peitsch, 2015; Phillips et al., 2016; Titz et al., 2016).

It was decided to focus the present study on a male population only to minimize the variability between genders.

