# 7.2.8.8 Nasal scraping, sical assessment and biological specimen collections for further analysis

See Appendix A - Schedule of Events for the timepoints of assessment.

Nasal scraping of the inferior turbinate of both nostrils will be performed on all 14 study participants as described in the separate document "Method establishment to obtain human nasal epithelial sample using the Rhino-probe".

For 4 study participants, nasal scraping (left nostril with method 1, right with method 2) will be performed and cell samples will be collected, processed, appropriately labeled and shipped by the study site as per the "Method establishment to obtain human nasal epithelial sample using the Rhino-probe" to the appropriate laboratory for further histological assessment.

For the 10 remaining study participants, 5 will undergo nasal scraping using method 1, and 5 using method 2. For all 10 study participants, cell sample from one nostril will be added into one buffer and cell sample from the other nostril into a second buffer. Samples will be collected, processed, appropriately labeled and shipped by the study site as per the "Method establishment to obtain human nasal epithelial sample using the Rhino-probe" to the appropriate laboratory for subsequent RNA quantity and quality analysis.

RNA quantity and quality will be assessed as per the Sponsor internal laboratory SOPs. RNA from the nasal sample will be extracted. Then a quantification step will occur using a Nanodrop 1000 instrument (TermoFisher scientific).

The quality will be assessed by using a Bioanlayzer 2100 (Agilent Technologies): the Bioanalyzer delivers a mark from 1 to 10 (10 is the best) to give an idea of the quality and integrity of the RNA (RIN value stands for RNA integrity Number).

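### In all four histology participants each scraping method is tied to one nostril, so the within-person histology comparison cannot separate method from side; the RNA comparison is unaffected (minor)

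*Protocol*

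**What the plan says.** Protocol section 4.1 (repeated in the synopsis, Study Design, and in section 7.2.8.8) divides the 14 participants into two subsets for nasal scraping.

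- **Histology, 4 participants.** Each person receives both methods, one per nostril, and the sides are fixed: "left nostril with method 1, right with method 2". Section 7.2.8.8 repeats it: "For 4 study participants, nasal scraping (left nostril with method 1, right with method 2". No place mentions swapping or randomising sides.
- **RNA, 10 participants.** "For the 10 remaining study participants, 5 will undergo nasal scraping using method 1, and 5 using method 2". Both nostrils of a person get the same method and differ only in buffer: "cells from one nostril will be added into one buffer, cells from the other nostril into a second buffer".

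Section 4.2 states what the two methods are compared for: to "identify and standardize the optimal one which results in the highest quantity and quality of" RNA. Section 3.2 lists histology collection and RNA evaluation as the two endpoints under secondary objective 1. Section 12.1 summarises RNA concentration and RIN by method. Section 13.6 sends the histology results to reports outside the CSR. In the SAP, the first block of Table A 9 labels its rows with the same pairing of left with method 1 and right with method 2.

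The full scraping procedure is in a separate Rhino-probe document that was not supplied.

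**The concern.** The four histology participants give the study's only within-person comparison of the two methods. Pairing is useful because the participant's own level drops out of the comparison. That benefit is lost if something else always differs between the two nostrils in the same direction as method, and here side always does.

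A side difference is possible, though the documents neither report nor exclude one. Scraping takes place on the inferior turbinate at the end of Visit 3. The saccharin test places a particle on the inferior turbinate four times that day and once at Visit 2, and section 7.2.8.7 does not name a nostril. If one nostril were used throughout (an assumption), the two scraped sides would have had different handling beforehand.

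At stake is whether a later histology report could attribute a difference between the paired samples to the method. The defect cannot be repaired once the samples are taken.

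**Working it through.** **The plan's own figure.** The only sample-size statement (protocol 12.2, SAP 5.1) concerns saccharin transit time: SD 2.5 min, difference 3.75 min, 7 per group. With two-sided 5% and an assumed power of 80%, n = 2 × (1.960 + 0.842)² × 2.5² / 3.75² = 6.98, so 7 per group (power 80.1% by normal approximation). It reproduces, but it plays no part in the scraping comparison.

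**Histology subset as planned.** Inputs from section 4.1: 4 participants, 8 nostrils, method 1 always left. Let τ be the effect of method 1 minus method 2, δ the left-minus-right effect, and σ² the residual variance per nostril.

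- Every left-minus-right difference has expectation τ + δ.
- The mean of the four estimates τ + δ, with variance 2σ²/4 = 0.5σ². Nothing in the data separates the two terms.
- A model with 4 participant terms, method and side has 6 columns and rank 5. The method-side correlation is 1.0.

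**Size of the bias.** It equals δ, which the documents do not give. The standard error of the mean difference is √0.5 σ = 0.71σ. Over an assumed range:

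| Assumed δ | Bias in τ | Bias / standard error |
|---|---|---|
| 0 | 0 | 0 |
| 0.25σ | 0.25σ | 0.35 |
| 0.5σ | 0.5σ | 0.71 |
| 1.0σ | 1.0σ | 1.41 |

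**Sides swapped in two of the four.** Order A has expectation τ + δ and order B has −τ + δ. The estimate of τ is (mean A − mean B)/2, with variance (2σ²/2 + 2σ²/2)/4 = 0.5σ². Rank is 6 of 6, the correlation is 0, and the bias from δ is removed. The variance is the same as now; fitting side takes one residual degree of freedom (2 instead of 3).

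**Other splits.** A 3+1 split gives correlation 0.5 and variance (2σ²/3 + 2σ²)/4 = 0.67σ². An independent coin flip per participant puts all four in the same order with probability 2 × 0.5⁴ = 12.5%. A prespecified 2+2 list is therefore better than unrestricted randomisation.

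**RNA subset.** Inputs from section 4.1: 10 participants, 20 nostrils, method constant within a person. Each method is used on 5 left and 5 right nostrils. The method-side correlation is 0, and intercept, method and side have rank 3 of 3. If one buffer were always used for one side, buffer and side would be aliased (rank 3 of 4 with buffer added), but method would remain estimable.

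**Smoking group in the RNA subset.** The supplied text gives no allocation rule. Assume histology takes 2 smokers and 2 never smokers, leaving 5 and 5, and that allocation is random. The C(10,5) = 252 allocations divide by number of smokers on method 1 (0 to 5) as 1, 25, 100, 100, 25, 1.

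- Complete separation of method by smoking group: 2/252 = 0.8%.
- A 4:1 split or worse: 52/252 = 20.6%.

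**The case against.** The strongest objection is that histology is not how the method will be chosen. Section 4.2 ties the choice to RNA yield and quality, and those data are balanced over sides. Neither protocol 12.1 nor SAP 5.5.4.1 plans a histology contrast between methods. The results go to a separate report, the study tests no hypotheses, and four pairs would be weak evidence even with sides balanced. All of this stands, and it limits the point to a minor one.

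A reader might go further in three ways that the documents do not support:

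- **That the study cannot choose between its methods.** The aliasing is confined to the four histology participants. Table A 9 has an RNA block for these four, although the protocol sends their samples to histology; that block pools both methods and shows no contrast.
- **That the RNA part has the same flaw.** It does not, because both nostrils get one method. The missing rules for smoking-group balance and for nostril-to-buffer assignment are separate matters. They are only not stated in the supplied text, and the Rhino-probe document may contain them.
- **That method could well coincide with smoking group.** The text does not exclude it, but under the assumptions above it has a 0.8% chance.

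It is also fair to say that no left-right difference is documented. That leaves the size of the bias unknown; it does not show it to be zero. The Rhino-probe document cannot remove the histology aliasing while the protocol itself fixes the sides.

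**Conclusion.** The point holds for the histology comparison alone. With method 1 on the left in 4 of 4 participants, a within-person difference in histology is the sum of a method effect and a side effect, and the two cannot be separated. The bias equals the side difference, whose size is not given. The RNA comparison named as the criterion for choosing the method is not affected.

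The aliasing follows from the protocol wording and needs no assumption. Its practical importance assumes that someone will compare the paired histology samples by method, which the secondary objective invites but no analysis section specifies. Severity is minor: an avoidable weakness in a secondary, descriptive endpoint, worth correcting because correction is nearly free and impossible after collection.

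**What to change.** In the synopsis, section 4.1 and section 7.2.8.8, replace the fixed sides with a prespecified list. Two of the four histology participants have method 1 left and method 2 right, and the other two have the reverse, ideally with one smoker and one never smoker in each order. Change the row labels in SAP Table A 9 so that side and method are recorded separately. The cost is a line of text in each place and a four-row list, with no added samples, visits or procedures.

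Optional, at similarly low cost: with 2 smokers and 2 never smokers in histology, allocate the remaining 5 smokers and 5 never smokers to method within smoking group (3+2 and 2+3), and alternate which nostril goes to which buffer. If the Rhino-probe document already sets these rules, a cross-reference is enough.
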